## LIST OF ABBREVIATIONS

Abbreviations pertain to the statistical analysis plan (SAP) only (not the tables, figures, and listings [TFLs]).

%AUC extrap	percentage extrapolation for area under the concentration-time curve extrapolated to infinity
ADaM	analysis data model
AE	adverse event
AUC	area under the concentration-time curve
AUC 0-24	area under the concentration-time curve from hour 0 to 24 hours postdose
AUC 0-inf	area under the concentration-time curve from hour 0 extrapolated to infinity
AUC 0-t	area under the concentration-time curve from hour 0 to the last measurable concentration
BLQ	below the limit of quantification
CDISC	Clinical Data Interchange Standards Consortium
CI	confidence interval
CL/F	apparent systemic clearance
C max	maximum observed plasma concentration
CRU	Clinical Research Unit
CSR	clinical study report
CTCAE	Common Terminology Criteria for Adverse Events
CV	coefficient of variation
ECG	electrocardiogram
EOS	End of Study
EOT	End of Treatment
ET	Early Termination
Geom CV	geometric CV
Geom Mean	geometric mean
ICF	Informed Consent Form
ICH	International Council for/Conference on Harmonisation of Technical Requirements for Registration of Pharmaceuticals for Human Use
λ Z	apparent terminal elimination rate constant
λ Z Lower	start of exponential fit
λ Z N	number of data points included in the log-linear regression
λ Z Span Ratio	time period over which λ Z was determined as a ratio of t 1/2
λ Z Upper	end of exponential fit
LSM	least squares mean
MedDRA	Medical Dictionary for Regulatory Activities

---

MRT inf	mean residence time based on area under the concentration-time curve from time 0 extrapolated to infinity
NC	not calculated
NR	not reported
PK	pharmacokinetic(s)
QTcF	QT interval corrected for heart rate using Fridericia's formula
R  -adj	adjusted coefficient for determination of exponential fit
SAE	serious adverse event(s)
SAP	statistical analysis plan
SD	standard deviation
TEAE	treatment-emergent adverse event
TFL	Table, figure, and listing
t 1/2	apparent plasma terminal elimination half-life
t max	time to maximum observed plasma concentration
V z /F	apparent volume of distribution at the terminal phase
WHODrug	World Health Organization Drug Dictionary

## 1. INTRODUCTION

This SAP has been developed after review of the clinical study protocol (Final Version 1.0 dated 1 December 2020) and electronic case report form.

This SAP describes the planned analysis of the pharmacokinetic (PK) and safety and tolerability data from this study. A detailed description of the planned TFLs to be presented in the clinical study report (CSR) is provided in the accompanying TFL shells document.

In general, the analyses are based on information from the protocol, unless they have been modified by agreement with Loxo Oncology, Inc. A limited amount of information about this study (eg, objectives, study design) is given to help the reader's interpretation. This SAP must be finalized prior to the lock of the clinical database for this study. When the SAP and TFL shells are approved, they will serve as the template for this study's CSR.

This SAP supersedes any statistical considerations identified in the protocol; where considerations are substantially different, they will be so identified. If additional analyses are required to supplement the planned analyses described in this SAP, they may be performed and will be identified accordingly in the CSR. Any substantial deviations from this SAP will be agreed with Loxo Oncology, Inc. and identified in the CSR.

This SAP is written with consideration of the recommendations outlined in the International Conference on Harmonisation (ICH) E9 guideline *Statistical Principles for Clinical Trials* and ICH E3 guideline *Structure and Content of Clinical Study Reports*.

The document history is presented in [Appendix 1](#).

## 2. STUDY OBJECTIVES

### 2.1.1. Primary Objective

The primary objective of the study is to assess the effect of food on the PK of a single oral dose of LOXO-305 under fasted and fed conditions in healthy adult subjects.

### 2.1.2. Secondary Objective

The secondary objective of the study is to assess the safety and tolerability of a single oral dose of LOXO-305 with and without food in healthy adult subjects.

## 3. STUDY ENDPOINTS

### 3.1. Primary Endpoints

The following PK parameters will be calculated whenever possible, based on the plasma concentrations of LOXO-305 (as appropriate):

- area under the concentration-time curve (AUC) from hour 0 to 24 hours postdose (AUC0-24)

- area under the concentration-time curve from hour 0 to the last measurable concentration ( $AUC_{0-t}$ )
- area under the concentration-time curve from hour 0 extrapolated to infinity ( $AUC_{0-\infty}$ )
- percentage extrapolation for  $AUC_{0-\infty}$  (% $AUC_{\text{extrap}}$ )
- apparent systemic clearance (CL/F)
- apparent plasma terminal elimination half-life ( $t_{1/2}$ )
- maximum observed plasma concentration ( $C_{\max}$ )
- time to maximum observed plasma concentration ( $t_{\max}$ )
- apparent terminal elimination rate constant ( $\lambda_z$ )
- apparent volume of distribution at the terminal phase ( $V_z/F$ )

### **3.2. Secondary Endpoints**

Safety and tolerability will be assessed by monitoring adverse events (AEs), performing physical examinations and clinical laboratory evaluations, measuring vital signs, and recording 12 lead electrocardiograms (ECGs).

## **4. STUDY DESIGN**

This is a Phase 1, open-label, randomized, 2-way crossover study to investigate the effect of food on the single oral dose PK of LOXO-305 in healthy adult subjects.

A single oral dose of LOXO-305 will be administered under fasted conditions (Treatment A) and fed conditions (Treatment B). PK sampling will be obtained for 168 hours after administration of each dose of LOXO-305 (ie, on Days 1 and 8). The 2 treatment sequences will be AB and BA. Subjects will be randomly assigned to 1 of the 2 treatment sequences, according to a randomization scheme issued by Covance. Up to 20 healthy adult male and female subjects (women of non-childbearing potential only) will be enrolled.

In Treatment A, a single oral dose of 200 mg LOXO-305 will be administered in the morning on Day 1 or Day 8 (according to the randomization scheme), following a fast of at least 10 hours prior to and 4 hours after dosing. Water will be restricted for 1 hour prior to and 1 hour after dosing with the exception of water administered for dose administration.

In Treatment B, a single oral dose of 200 mg LOXO-305 will be administered in the morning on Day 1 or Day 8 (according to the randomization scheme), approximately 30 minutes after starting a high-fat breakfast. Water will be restricted for 1 hour prior to and 1 hour after dosing with the exception of water administered for dose administration. High-fat breakfasts should be entirely consumed within 30 minutes.

Blood samples for the analysis of plasma concentrations of LOXO-305 will be collected from predose through 168 hours postdose for Treatment A and Treatment B.

There will be a washout period of 7 days between the doses of LOXO-305 administered in Treatments A and B.

[figure not shown]
A schematic of the study design is presented in [Figure 1](#). The start of the study is defined as the date the first subject who is enrolled in the study signed an Informed Consent Form (ICF). Note that enrolled subjects are defined as those subjects who are assigned to receive a dose of study drug; this definition excludes screen failure subjects. Replacement subjects may be enrolled only if deemed necessary by the Sponsor.

Subjects who are determined to be screen failures are permitted to be re-screened if the Investigator (or designee), with agreement from the Sponsor, feels that the subject may meet eligibility criteria upon re-screen. Re-screened subjects will be provided a new subject number.

To assess their eligibility to enter the study, potential subjects will be screened within 28 days (Days -29 to -2) and be admitted to the Clinical Research Unit (CRU) on Day -1 (Check-in).

Subjects will be confined at the CRU from the time of Check-in (Day -1) until End of Treatment (EOT) on Day 15 upon completion of all PK and safety assessments or Early Termination (ET) if the subject discontinues. Subjects will be dosed on Day 1 and Day 8. A follow-up phone call will occur for all subjects who received at least 1 dose of study drug (including subjects who are terminated early) 7 days ( $\pm$  2 days) after EOT or ET. The duration of participation is expected to be approximately 53 days (Screening through follow-up phone call).

### Figure 1: Study Design

Abbreviations: EOT = End of Treatment; ET = Early Termination; ICF = Informed Consent Form; PK = pharmacokinetic.

In this study, physical examinations, 12-lead ECGs, vital sign measurements, How Do You Feel? Inquiries, clinical chemistry panel, coagulation parameters, hematology panel,

urinalysis, and recording of concomitant medications will be performed at specific times during the study.

The AEs and serious adverse events (SAEs) will be collected beginning at informed consent. The AEs will be reported throughout the study (ie, from signing of the ICF until End of Study [EOS], or until ET if the subject discontinues from the study and does not complete a follow-up phone call), either as subject medical history (if the event is reported as beginning prior to signing of the ICF or if the event occurs prior to study drug administration on Day 1 and is assessed as not related to study procedures by the Investigator [or designee]) or as AEs (if the event occurs after signing of the ICF but prior to study drug administration on Day 1 and is assessed as related to study procedures by the Investigator [or designee], or if the event occurs after study drug administration on Day 1 through EOT or ET regardless of relationship to study drug). From EOT or ET through EOS, only AEs assessed as related to study drug by the Investigator (or designee) are to be reported. All SAEs that develop from the time of ICF signing until EOS (or ET, if the subject discontinues from the study and does not complete a follow-up phone call) are to be reported.

Study completion is defined as the time of the last subject's follow-up phone call.

## 5. SAMPLE SIZE JUSTIFICATION

Up to **CC1** healthy adult male and female subjects (women of non-childbearing potential only) will be enrolled. This is a Phase 1 study and the sample size is consistent with previous studies of a similar design. Up to **CC1** subjects are anticipated to be sufficient to provide a reliable estimate of the magnitude and variability of the food effect. The highest within-subject coefficient of variation (CV) observed in LOXO-BTK-20014 was **CC1** for  $C_{max}$ . A sample size of **CC1** will provide approximately 80% power to have the respective 90% confidence intervals (CIs) for the geometric mean ratios for  $C_{max}$  and AUC values between fed and fasted treatments are within the interval of 80.00% to 125.00%, assuming a within-subject CV of **CC1** and that the expected ratio of means is **CC1**. Replacement subjects may be enrolled only if deemed necessary by the Sponsor.

Every attempt will be made to enroll at least 3 subjects of each sex in the study.

## 6. STUDY TREATMENTS

The study treatment names, abbreviations, and ordering to be used in the TFLs are presented in [Table 1](#).

**Table 1: Presentation of Study Treatments in TFLs**

Study Treatment	Abbreviation	Order in TFLs
200 mg LOXO-305 (Fasted)	A	1
200 mg LOXO-305 (Fed)	B	2

The study treatment sequence names, abbreviations, and ordering to be used in the TFLs are presented in [Table 2](#).

**Table 2: Presentation of Study Treatment Sequences in TFLs**

Study Treatment Sequence	Abbreviation	Order in TFLs
200 mg LOXO-305 (Fasted) on Day 1/	AB	1
200 mg LOXO-305 (Fed) on Day 8/		
200 mg LOXO-305 (Fed) on Day 1/	BA	2
200 mg LOXO-305 (Fasted) on Day 8/		

All treatments described above are the planned treatments. The TFLs will reflect the actual treatments received.

## 7. DEFINITIONS OF POPULATIONS

Any protocol deviations, including those related to COVID-19, will be considered prior to database lock for their importance and taken into consideration when assigning subjects to populations.

### 7.1. All Subjects Population

The all subjects population will include all subjects who signed the ICF and had any study assessment recorded in the database per the protocol.

### 7.2. Safety Population

The Safety Population will consist of all subjects who have received at least 1 dose of LOXO-305. Subjects will be classified into groups based on actual treatment received.

### 7.3. Pharmacokinetic Population

The PK Population will consist of all subjects who have received 1 dose of LOXO-305, have at least 1 quantifiable plasma concentration, and for whom at least 1 PK parameter can be computed. A subject may be excluded from the PK summary statistics and statistical analysis if the subject has an AE of vomiting that occurs at or before 2 times the median  $t_{max}$ . The impact of protocol deviations on the PK population will be evaluated on a case-by-case basis.

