8.2. Analysis Populations

The **PK Population** will consist of all subjects who have received a dose of study drug, have at least 1 quantifiable plasma concentration, and for whom at least 1 PK parameter can be computed. A subject may be excluded from the PK summary statistics and statistical analysis if the subject has an AE of vomiting that occurs at or before t_{max}. The impact of protocol deviations on the PK population will be evaluated on a case-by-case basis.

The **Safety Population** will consist of all subjects who have received at least 1 dose of study drug. Subjects will be classified into groups based on actual treatment received.

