#### **8.5.1.4. Treatment of Outliers in Pharmacokinetic Analysis**

If a value is considered to be anomalous due to being inconsistent with the expected PK profile, it may be appropriate to exclude the value from the PK analysis. However, the exclusion of any data must have strong justification and will be documented in the CSR.

Any quantifiable predose concentration value for LOXO-305 on Day 1 will be considered anomalous and set to missing for the PK analysis.

If the predose concentration is >5% of  $C_{max}$  in the second period, all PK concentration and parameter data will be excluded from the summary statistics and statistical analysis for that period.

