### 8.5.3.1. Statistical Analyses

A statistical analysis will be conducted to investigate the food effect on the treatment by comparing Treatment B (Fed) to Treatment A (Fasted) for  $AUC_{0-t}$ ,  $AUC_{0-inf}$ , and  $C_{max}$ , using Treatment A as reference.

The natural log (ln)-transformed PK parameters will be analyzed using a mixed model. The model will include planned treatment sequence, period, and actual treatment as fixed effects, and subject within planned treatment sequence as a random effect.

For each PK parameter separately, the least squares mean (LSM) for each treatment, difference in LSMSs between the fed and fasted treatments, and corresponding 90% CIs will be calculated; these values will then be back-transformed to give the geometric least square mean (GLSM), ratio of GLSMs, and corresponding 90% CIs.

For each PK parameter separately, it will be concluded that there is absence of a food effect on the treatment if the 90% CI for the ratio of GLSMs is completely contained within the predefined interval of (80.00%, 125.00%). This procedure is equivalent to Schuirmann's two one-sided tests at the 0.05 level of significance.

Additionally, the pooled estimate (across all treatments) of the within-subject coefficient of variation (CV) will be calculated, and residual plots will be produced to assess the adequacy of the model(s) fitted.

Example of the SAS code that will be used is as follows:

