### **10. SIGNIFICANT CHANGES FROM THE PROTOCOL-SPECIFIED ANALYSES**

There were no significant changes from the protocol-specified analyses.

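### Does the optional exclusion of a vomiting subject in SAP 7.3 leave the food-effect conclusion open to choice?

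*SAP*

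**What the plan says.** SAP 7.3 defines the PK population and then makes exclusion optional: "A subject may be excluded from the PK summary statistics and statistical analysis". The trigger for using that option is a subject who "has an AE of vomiting that occurs at or before 2 times the median" tmax. Protocol 8.2 has the same optional, subject-level wording, but its window ends at tmax itself. SAP Section 1 settles which text governs: "This SAP supersedes any statistical considerations identified in the protocol". SAP Section 10 states: "There were no significant changes from the protocol-specified analyses". The document history in SAP Appendix 1 records only the added period effect.

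Four other places bear on the point:

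- SAP Section 7, which introduces the populations: "Any protocol deviations, including those related to COVID-19, will be considered prior to database lock for their importance". Vomiting is not named.
- SAP 8.5.1.4 asks for strong justification, and documentation in the study report, when data are excluded. The context is anomalous values. The same section has one mandatory rule, for second-period predose concentrations above 5% of Cmax: "all PK concentration and parameter data will be excluded from the summary statistics and statistical analysis for that period".
- SAP 8.5.3 keeps excluded subjects visible in the PK parameter tables and marks them as excluded. SAP 8.1 lists all captured data.
- SAP 8.5.3.1 sets the decision: "it will be concluded that there is absence of a food effect on the treatment if the 90% CI" for the ratio lies wholly within 80.00% to 125.00%.

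**The concern.** An option to exclude, in a small open-label crossover with a pass/fail conclusion, looks like a choice that could be made after the subject's exposure has been seen. A vomiter retained in the fed period pulls the fed/fasted ratio down; one retained in the fasted period pushes it up. If the true ratio sits at the upper limit of 1.25, keeping a fed-period vomiter makes a wrong finding of no food effect more likely. The mandatory predose rule in SAP 8.5.1.4 shows that the authors could write a firm rule. The move from tmax to twice the median tmax is also not listed in SAP Section 10. At stake would be the credibility of the primary conclusion.

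**Working it through.** **Inputs.** Protocol 8.1: 20 subjects, 10 per sequence, within-subject CV 20.9% (for Cmax, the highest seen in LOXO-BTK-20014), expected ratio 1.05, limits 80% to 125%, about 80% power. SAP 8.5.3.1: 90% CI, two one-sided tests at 0.05. The exposure left after vomiting is not in the documents; it is an assumption, shown from 0.8 down to 0.3 of normal.

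**1. The plan's own power.** The log-scale SD is √ln(1 + 0.209²) = 0.2068. SE = 0.2068 × √(0.5 × (1/10 + 1/10)) = 0.0654, with 18 degrees of freedom. Integrating over the estimated SD gives 81.2% power, which agrees with the stated 80%. With one subject dropped (10 + 9) it is 78.8%.

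**2. Keep versus drop, given one vomiter.** Each simulated trial at true ratio 1.05 was analysed with the subject kept (n = 20) and dropped (n = 19). Share of trials in which the two conclusions differ:

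| Exposure factor | Vomiting in fed period | Vomiting in fasted period |
|---|---|---|
| 1.0 (no loss) | 5.9% | 6.0% |
| 0.8 | 7.0% | 7.6% |
| 0.5 | 12.5% | 23.8% |
| 0.3 | 26.2% | 51.9% |

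The first row is what removing any healthy subject does. Only the excess over about 5.9% is due to vomiting.

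**3. How often it would arise.** Protocol 1.4 counts healthy volunteers as 10 + 27 + 24 + 9 + 15 = 85. Protocol 1.4.1 reports vomiting in 1 of them (partly preliminary data). The chance of at least one vomiter among 20 is 1 − (84/85)²⁰ = 21.1%. The exact 95% interval for 1/85 (0.03% to 6.4%) turns this into 0.6% to 73%.

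**4. Added chance of a different conclusion.**

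- Factor 0.5, all vomiting in the fed period: 0.211 × (12.5 − 5.9) = 1.4%.
- Factor 0.5, all in the fasted period: 0.211 × (23.8 − 5.9) = 3.8%.
- Factor 0.8: 0.211 × 1.1 = 0.2% and 0.211 × 1.7 = 0.4%.
- Factor 0.3: 0.211 × 20.3 = 4.3% and 0.211 × 46.0 = 9.7%.

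These treat every vomiting event as falling inside the window. Protocol 1.4.1 gives no onset time for the one known event, so at this vomiting rate they are upper figures for each factor.

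**5. False conclusion at the limit.** At true ratio 1.25, keeping a fed-period vomiter at factor 0.5 raises the chance of wrongly concluding no food effect from 5.0% to 8.9%. Weighted by the chance of a vomiter, and taking half of them as fed-period, this adds 0.211 × 0.5 × 3.9 = 0.4 percentage points.

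**6. Endpoint.** The 20.9% CV belongs to Cmax. Vomiting after a subject's own tmax cannot lower a peak already reached, so for Cmax the later part of the window matters little. AUC has a CV no higher than 20.9%. At assumed CVs of 15% and 10% with factor 0.5, the gross disagreement is 2.4% and 0.0% (fed), and about 18% and 3.8% (fasted).

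**7. What a firm rule would gain.** Dropping only the affected period gives 79.1% power, against 78.8% for dropping the whole subject: 0.3 points.

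**The case for a change.** The strongest argument for a change is that none of the safeguards is written for this case. A vomiting AE is not a protocol deviation, so the pre-lock review does not plainly cover it. The justification requirement in SAP 8.5.1.4 constrains exclusion but not retention, and retention is the choice that can inflate a false finding of no food effect. Listing excluded subjects discloses the choice without fixing it in advance. With severe loss in the fasted period, one subject can reverse the result: with the other 19 subjects at ratio 1.05, the interval is 93.4% to 118.0% with the subject dropped and 95.8% to 129.8% with the subject kept at factor 0.3.

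Much of this stands as description. The median is undefined, the option has no selection rule, and the changed window is not listed. It does not amount to a defect. The disagreement rates measure how far keeping differs from dropping; a mandatory rule would choose one of the two and leave that difference in place. Bias arises only if the choice follows the result, and nothing in the documents says it would. A rule based on this study's treatment medians could not be applied until concentrations were available, so a decision wholly blind to exposure is hard to obtain that way. Mandatory exclusion would also discard periods in which little or no drug was lost.

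**Conclusion.** The plan can stand. SAP 7.3 has a time trigger, and what it leaves open (whose median, one period or both, when to decide) is what a pharmacokineticist and statistician settle case by case and document. Because the data are listed and excluded subjects are marked, a reader can see the choice and repeat the analysis the other way. Optional, documented exclusion against a mandatory rule is a fair trade-off. The different window in protocol 8.2 is resolved by the SAP's precedence, and an entry in Section 10 would alter no result.

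The added chance of a different conclusion is about 1.4% (fed) to 3.8% (fasted). This rests on exposure being halved, a vomiting rate of 1 in 85 and every event falling inside the window. It shrinks to 0.2% to 0.4% for mild loss and reaches 9.7% for a 70% loss in the fasted period. The vomiting rate is poorly known: at the upper limit of its interval, the 3.8% would become 0.73 × 17.9 = 13%. Those extremes call for care if a case occurs, not for different text now.

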## 8. STATISTICAL METHODOLOGY

### 8.1. General

Listings will be provided for all data captured in the database. Listings will include all subjects assigned to the all subjects population and include data up to the point of study completion or discontinuation. Subjects are generally considered to have completed the study if they completed all protocol-specified procedures and assessments for the EOT visit. Any subject who discontinued the study will be identified accordingly in the listings. Summaries and statistical analyses will include the subjects assigned to the relevant population based on data type.

Data analysis will be performed using the SAS® statistical software package Version 9.4 (or higher if upversioned during the study).

Analysis Data Model (ADaM) datasets will be prepared using Clinical Data Interchange Standards Consortium (CDISC) ADaM Version 2.1 (or higher if upversioned during the study) and CDISC ADaM Implementation Guide Version 1.2 (or higher if upversioned during the study). Pinnacle 21 Community Validator Version 3.1.0 (or higher if upversioned during the study) will be utilized to ensure compliance with CDISC standards.

Where reference is made to 'all calculations', this includes, but is not limited to, summary statistics, statistical analyses, baseline derivation and changes from baseline, and any parameter derivations.

